1.0 PROTOCOL SUMMARY AND/OR SCHEMA

Protocol title:	Phase II trial of sorafenib for patients with metastatic or recurrent esophageal and gastroesophageal junction cancer
Study objectives Primary:	To evaluate the 2-month progression-free survival (PFS) of sorafenib in patients with metastatic or recurrent esophageal and gastroesophageal (GE) junction cancer. With a total of 35 patients, we have 90% power to detect an improvement in the 2-month PFS from a historical control of 50% to 70% with type I error rate of 10%.
Secondary:	a) To evaluate the overall response rate of sorafenib in the evaluable population;
	b) To evaluate the tolerability and adverse event profile of sorafenib in this patient population;
	c) To perform an exploratory analysis of differential response between squamous cell carcinoma and adenocarcinoma.
	d) To evaluate phosphorylated extracellular signal-regulated kinase (pERK) expression in tumor tissue and correlate with tumor control.
Study population:	Patients with metastatic or recurrent esophageal or GE junction squamous cell carcinoma or adenocarcinoma will be eligible. Patients will be allowed to have up to two prior chemotherapy regimens for metastatic disease or up to three prior therapies if they also received neoadjuvant/adjuvant chemotherapy or chemoradiotherapy. Prior therapy must be completed at least three weeks prior to initiation of sorafenib therapy.
Study design:	Single instutition, open-label, non-randomized, single-arm phase II
Number of patients:	: 35
Study drugs:	Sorafenib, administered orally
Dose and regimen:	Sorafenib 400 mg twice daily administered continuously. Patients will continue on treatment until progression of disease. Each cycle consists of 28 days. A CT (computerized tomography) or MRI (magnetic resonance imaging) scan of the chest and abdomen will be obtained at baseline, after the first four weeks of therapy, at eight weeks, and then every eight weeks

IRB PB

IRB#:09-016A(9)

thereafter. The same imaging modality performed at baseline (CT or MRI) will be repeated at subsequent imaging.

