4.2 Intervention

35 patients will be enrolled on this clinical trial. Patients will receive sorafenib 400 mg BID continuously until disease progression, unacceptable toxicity or serious intercurrent illness develops or if patient consent is withdrawn.

The primary endpoint will be 2-month progression-free survival (PFS). With a total of 35 patients, we have 90% power to detect an improvement in the 2-month PFS from a historical control of 50% to 70% with type I error rate of 10%. Secondary endpoints include the response rate to sorafenib and its toxicity. Our basis for PFS estimate in this patient population comes from our prior phase II trial of erlotinib in esophageal cancer (which had essentially no activity in adenocarcinoma of the esophagus), and nearly identical PFS results reported for this patient population treated with either erlotinib or gefitinib (1.6-2.0 months PFS in all studies) (54-56).

Patients must have measurable disease and will undergo a computerized tomography (CT) or magnetic resonance imaging (MRI) scan of the chest and abdomen at baseline, after the first four weeks of therapy, at eight weeks, and every eight weeks thereafter, with a scheduling window of up to one to fourteen (1-14) days. If a complete response is achieved and

IRB#:09-016A(9)

maintained for 12 months, patients with complete response will then be required to repeat CT or MRI evaluation every 4 months up to 5 years post complete response status, then every 6 months thereafter, with a scheduling window of up to one to fourteen (1-14) days. Response assessment will be by RECIST criteria.⁴⁵ The same imaging modality performed at baseline (CT or MRI) will be repeated at subsequent imaging.

Therapy will be administered in the outpatient setting, with each cycle consisting of 28 days of continuous therapy. The cycle start date will coincide with the physician visit date. A study diary will be completed by patients to ensure compliance with the study drug (see Appendix A).

Patients will be required to take antacid therapy to reduce the potential for gastrointestinal bleeding. Allowable agents include but are not limited to ranitidine, omeprazole, carafate or similar agents.

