14.0 BIOSTATISTICS

This is a single institution, open-label, non-randomized, single-arm phase II evaluation. The primary objective of this study is to determine the 2-month progression free survival (PFS) for patients with advanced or recurrent esophageal and gastroesophageal (GE) junction cancer who are treated with sorafenib 400 mg twice daily. PFS is defined in Section 12.6.

The historical control 2 month PFS for patients with untreated advanced esophageal and GE junction cancer is approximately $50\%^{29}$. Using an exact binomial single stage design we require 35 patients to differentiate between 2-month PFS of 50% and 72% with type I and II error rates of 10% each. If 22 or more patients are alive and progression free at 2 months, the regimen is declared promising. With a total of 35 patients, we also have approximately 89% power to detect an improvement in the response rate from 5% to 18% with a type I error rate of 10%.

If at any time there are 14 or more deaths or progressions before 2 months then the trial will close as it is mathematically impossible to achieve the desired endpoint.

We assume an accrual rate of 1-2 patients per month for a study duration of 18-35 months.

Secondary endpoints involve an assessment of the overall response rate (complete and partial responses), as determined by RECIST criteria. Toxicities will also be assessed and tabulated. While the small sample size precludes any definitive conclusions about differential responses based on the squamous cell carcinoma and adenocarcinoma histologies, any differences observed between the two histologies may be exploratory and hypothesis-generating. Finally, tumor tissue will undergo immunohistochemical staining for phosphorylated extracellular signal-regulated kinase (pERK). Any differential response based on different levels of pERK tumor expression will similarly be hypothesis-generating. Fisher's exact test will be employed to investigate these exploratory analyses.

IRB#:09-016A(9)

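### Sections 1.0 and 4.2 claim 90% power at a 2-month PFS of 70%, but the 22-of-35 rule gives 86.5% there, and Section 14.0 uses 72%

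*Combined protocol and SAP*

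**What the plan says.** Section 1.0, in the primary objective, states that with 35 patients "we have 90% power to detect an improvement in the 2-month PFS from a historical control of 50% to 70" percent, with a type I error of 10%. Section 4.2 makes the same statement after saying that "35 patients will be enrolled on this clinical trial". Neither section names a test or a cutoff.

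Section 14.0 gives the operative design. It says: "we require 35 patients to differentiate between 2-month PFS of 50% and 72% with type I and II error rates of 10% each". It describes an exact binomial single-stage design and sets the decision rule: "If 22 or more patients are alive and progression free at 2 months, the regimen is declared promising". It adds an early-closure rule: "If at any time there are 14 or more deaths or progressions before 2 months then the trial will close".

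The null rate (50%), the sample size and the nominal error rates therefore agree in all three places. The alternative does not: 70% in Sections 1.0 and 4.2, and 72% in Section 14.0. Nothing in the protocol explains the difference.

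**The concern.** A single-arm trial with a fixed sample size and cutoff has one power at each true rate. If 35 patients give about 90% power at 72%, they must give less at 70%, so the two statements cannot both describe the same rule. The less demanding claim, that a smaller improvement can be detected with the same power, stands in the summary and the design section, where many readers look first.

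At stake is the meaning of a result that falls short of 22. Someone relying on Section 1.0 would take the chance of missing a true 2-month PFS of 70% to be 10%. If the rule's actual power is lower, that risk is understated.

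**Working it through.** **Inputs**

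- n = 35 (Sections 1.0, 4.2 and 14.0)
- Null rate p0 = 0.50 (all three sections)
- Alternative p1 = 0.70 (Sections 1.0 and 4.2) or 0.72 (Section 14.0)
- Type I error limit 0.10 and power target 0.90 (all three sections)
- Rule: success if X ≥ 22, exact binomial, single stage (Section 14.0)

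**Formula.** With X ~ Binomial(35, p), the probability of declaring success is P(X ≥ r | p) = Σ C(35, k) p^k (1 − p)^(35 − k), summed over k = r, …, 35. At p = p0 this is the type I error, and at p = p1 it is the power.

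**Step 1: reproduce Section 14.0.** P(X ≥ 22 | 0.50) = 0.0877 and P(X ≥ 22 | 0.72) = 0.9151. The type II error is 1 − 0.9151 = 0.0849. Both errors are under 10%, and a search over n shows that 35 is the smallest exact single-stage sample size for 50% versus 72%. Section 14.0 is correct.

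**Step 2: test the claim in Sections 1.0 and 4.2.** P(X ≥ 22 | 0.70) = 0.8650. The type II error is 1 − 0.8650 = 0.1350. The stated 90% is missed by 90.0 − 86.5 = 3.5 percentage points.

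**Step 3: try other cutoffs at n = 35.**

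| Cutoff | Type I error at 50% | Power at 70% | Power at 72% |
|---|---|---|---|
| 21 | 0.1553 | 0.9269 | 0.9578 |
| 22 | 0.0877 | 0.8650 | 0.9151 |
| 23 | 0.0448 | 0.7729 | 0.8454 |

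A cutoff of 21 reaches the power but breaks the 10% type I limit, and any lower cutoff breaks it further. A cutoff of 22 or more keeps the limit but has at most 86.5% power at 70%. No cutoff satisfies both.

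**Step 4: the early-closure rule.** After 14 failures at most 35 − 14 = 21 successes are possible, so 22 is already out of reach. The rule stops only trials that would fail anyway and leaves power unchanged.

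**Step 5: where the rule does reach 90%.** Solving P(X ≥ 22 | p) = 0.90 gives p = 0.7133, about 71.3%.

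**Step 6: what 70% with 90% power would need.** The smallest exact single-stage design for 50% versus 70% at 10%/10% is n = 39 with success at 24 or more (type I error 0.0998, power 0.9056).

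**Step 7: could 90% come from an approximation?** With n = 35, p1 − p0 = 0.20 and one-sided z = 1.2816:

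- Null and alternative variances: (0.20√35 − 1.2816 × 0.5)/√0.21 = 1.184, power 88.2%
- Alternative variance only: 0.20√35/√0.21 − 1.2816 = 1.300, power 90.3%
- Null variance only: 0.20√35/0.5 − 1.2816 = 1.085, power 86.1%
- Arcsine: 87.6%
- Continuity-corrected: 84.1%

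Two-sided versions give 72.7% to 82.6%.

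**The case against.** The strongest reply is that the section governing the analysis is right. Section 14.0 meets its own error limits, its closure rule matches its cutoff, and nothing done in the trial depends on the 70% figure. That stands: this is a wrong statement about a sound design, and false-positive control is not affected.

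A second reply is that Sections 1.0 and 4.2 name no test, so their 90% may be a large-sample approximation or a rounded summary. One formula does give 90.3%. That may explain the origin of the figure, but it does not support it. The trial will be judged by the exact rule in Section 14.0, whose power at 70% is 86.5%. Nor is 70% a harmless rounding of 72%: the rule reaches 90% only at about 71.3%, and the rounding favours the design.

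A third reply is that 3.5 points of power is a small gap and that no section says how a negative result will be read. The gap is indeed modest in absolute terms, and the concern about interpretation is a foreseeable reading, not a statement in the protocol. Neither point makes the power figure correct.

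**Conclusion.** The concern holds. Sections 1.0 and 4.2 attribute to the design a power it does not have, and they contradict Section 14.0 on the alternative for the primary endpoint. Exact power at 70% is 86.5%, not 90%. The chance of missing a true 70% rate is 13.5%, not 10%, which is about one third higher in relative terms (13.5/10 = 1.35).

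The conclusion assumes that the rule in Section 14.0 is the one that will be applied, and that all 35 patients contribute a yes-or-no outcome at 2 months. It does not call into question the sample size, the cutoff of 22, the early-closure rule or the type I error of 8.8%.

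**What to change.** Make Sections 1.0 and 4.2 agree with Section 14.0 by replacing 70% with 72% as the alternative. It would help to give the rule (22 or more of 35) with its exact properties: type I error 8.8% and power 91.5%. If 70% is the rate the investigators want to quote, keep it and state 86.5% power in both places, adding the same figure to Section 14.0 so that the sections match.

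Keep the sample size at 35 and the cutoff at 22. The 39-patient design would be needed only if both 70% and 90% power were to be kept, and nothing here requires that. The change costs wording only. The stated detectable difference, or the stated power, becomes slightly less favourable.

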2.0 OBJECTIVES AND SCIENTIFIC AIMS

Primary objective:

To evaluate the 2-month progression-free survival (PFS) of sorafenib in patients with metastatic or recurrent esophageal and gastroesophageal (GE) junction cancer.

Secondary objectives:

a) To evaluate the overall response rate (partial response and complete response) of sorafenib.

b) To evaluate the tolerability and adverse event profile of sorafenib in this patient population.

c) To perform an exploratory analysis of differential response between squamous cell carcinoma and adenocarcinoma.

d) To evaluate phosphorylated extracellular signal-regulated kinase (pERK) expression in tumor tissue and correlate with tumor response.

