12.2 Definitions

Response and progression will be evaluated in this study using standard Response Evaluation Criteria in Solid Tumors (RECIST) criteria.⁴⁵ Changes in only the largest diameter (unidimensional measurement) of the tumor lesions are used in the RECIST criteria. Note: Lesions are either measurable or non-measurable using the criteria provided below. The term "evaluable" in reference to measurability will not be used because it does not provide additional meaning or accuracy.

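### The synopsis limits the secondary response rate to an undefined evaluable population, so patients who fail before a follow-up scan could leave the denominator and raise the reported rate

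*Combined protocol and SAP*

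**What the plan says.** Three places in the combined protocol and SAP describe the response-rate objective or its size.

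- Section 1.0 (protocol summary), secondary objective a: "To evaluate the overall response rate of sorafenib in the evaluable population".
- Section 2.0, secondary objective a: "To evaluate the overall response rate (partial response and complete response) of sorafenib". No population is named.
- Section 14.0: "With a total of 35 patients, we also have approximately 89% power to detect an improvement in the response rate". The null and alternative rates given there are 5% and 18%, and the type I error is set at 10%. The later sentence in that section describing the secondary endpoint refers to RECIST but names no denominator.

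Planned enrolment is the same 35 (Section 4.2: "35 patients will be enrolled on this clinical trial"), with no allowance for patients who cannot be assessed and no replacement rule.

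The only other text on the word itself is in Section 12.2, where the term evaluable "in reference to measurability will not be used because it does not provide" extra information. That concerns how lesions are described. It does not define an analysis population.

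**The concern.** A single-arm, open-label trial that compares its response rate with fixed benchmarks needs its denominator settled in advance. Here the synopsis names a subset, no section says who belongs to it, and the other two statements do not repeat it. The choice could therefore be made after the responses are known.

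The direction of the effect is predictable. Section 4.2 requires measurable disease of everyone, so absence of baseline disease cannot be what the word screens out. The usual remaining meaning is that a patient had an adequate follow-up assessment. Patients who lack one through early death, clinical decline or stopping treatment have not shown a response. Removing them lowers the denominator and leaves the numerator unchanged.

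Other sections do not close the gap:

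- Section 12.4.3 labels some patients who stop without objective progression as symptomatic deterioration, but does not say whether they stay in the response denominator. Its best-response table has no row for patients never assessed.
- Section 12.5.1 requires confirmation at least four weeks after response is first seen, so a patient can also leave between the two scans.
- Section 12.6 says how patients who come off study are handled for progression-free survival. Response rate has no counterpart.

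The exploratory Fisher's exact comparisons of response by histology and by pERK (Section 14.0) inherit the same uncertainty.

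**Working it through.** **Inputs.** From Section 14.0: n = 35, null rate 5%, alternative rate 18%, type I error 10%, stated power about 89%. The exact binomial single-stage method is named there for the primary endpoint; I assume it carries over to response rate. Sidedness is not stated; I take the upper tail. The number evaluable is not given anywhere; I show 32, 30 and 28 as assumptions.

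**Step 1: reproduce the plan's power.** For a cut-off of r responders,

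P(X ≥ r) = 1 − Σ (k = 0 to r−1) C(35,k) p^k (1−p)^(35−k).

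| Cut-off r | Alpha (p = 0.05) | Power (p = 0.18) |
|---|---|---|
| 3 | 25.4% | 96.4% |
| 4 | 9.6% | 89.7% |
| 5 | 2.9% | 78.0% |

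The smallest cut-off that keeps alpha at or below 10% is 4. It gives power 89.7%, which agrees with the plan's figure. The cut-off of 4 is derived here; the plan states no decision rule for response.

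**Step 2: effect on the estimate.** If m patients are kept and all those left out are non-responders, the observed rate is x/m instead of x/35, so it is multiplied by 35/m.

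| Kept, m | Multiplier 35/m | Rate with 4 responders |
|---|---|---|
| 35 | 1.00 | 4/35 = 11.4% |
| 32 (assumed) | 1.09 | 4/32 = 12.5% |
| 30 (assumed) | 1.17 | 4/30 = 13.3% |
| 28 (assumed) | 1.25 | 4/28 = 14.3% |

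**Step 3: effect on the test.** Under the same mechanism the responder count does not change, so observing 4 or more responders is the same event whether the denominator is 35 or m. The cut-off does not move either: a cut-off of 3 with a 5% null already has alpha 12.7% at m = 25, and more at larger m, so 4 remains the smallest admissible value from 25 to 35. Against the all-patient rates, alpha stays at 9.6% and power at 89.7%. The harm is to the estimate, not to the error rates.

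**The case against.** The strongest reply is that this is one undefined word in a synopsis. Section 2.0 omits it, and a reader could take it to mean all treated patients with measurable disease, which is everyone. Most early progression would be seen on the four- or eight-week scan, and a patient progressing there is an assessed non-responder who stays in the denominator. Eligibility requires a life expectancy above three months. Nothing in the documents shows that five or seven of 35 patients would go unscanned, and response is a secondary endpoint.

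Much of that stands. The size of the inflation is unknown, and the historical 2-month progression-free survival of about 50% does not tell us how many patients would lack a scan. But if the phrase means everyone, it does no work and can be deleted without loss. If it means a subset, the documents neither say which nor count the unassessed as non-responders.

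Two stronger readings are tempting and should be resisted.

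- A reader might infer that the 89% power is wrong. It is not; it reproduces at 35. Lower figures, such as 81.4% with 30 patients or 76.8% with 28, require the 5% and 18% rates to apply inside the evaluable subset, as well as an assumed size for it. That premise cannot be combined with the claim that those removed are all non-responders, under which power is unchanged.
- A reader might infer that the plan states two conflicting denominators. Section 14.0 uses 35 as the basis for power and does not declare it the analysis set; Section 2.0 is silent. Only the synopsis names a population.

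**Conclusion.** The point holds as a question of denominator and estimate. The synopsis restricts response rate to a population the documents never define, the restriction is absent from Sections 2.0 and 14.0, and no rule says how unassessed patients count. On the usual reading, the reported rate can only be raised: by a factor of 35/m, or from 11.4% to between 12.5% and 14.3% for four responders if 28 to 32 patients are kept. This rests on two assumptions: that evaluable means having a follow-up assessment, and that the number kept lies in that range.

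The sample size, the stated response-rate power and the primary rule (22 or more of 35 alive and progression-free at 2 months) are not affected. The change is worth making because it is cheap and removes a choice that could otherwise be made after the data are seen.

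**What to change.** Delete the restriction to the evaluable population from secondary objective a in Section 1.0. State in Sections 1.0, 2.0 and 14.0 that response rate is confirmed complete plus partial response among all patients who start sorafenib, with any patient lacking a follow-up scan counted as a non-responder. An evaluable-only rate may be reported beside it if it is defined and labelled as supportive.

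The cost is wording in three sections, and a reported rate that may be slightly lower. The power sentence in Section 14.0 can stay as it is, since all 35 planned patients would then be the denominator it assumes, provided all 35 start treatment.

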2.0 OBJECTIVES AND SCIENTIFIC AIMS

Primary objective:

To evaluate the 2-month progression-free survival (PFS) of sorafenib in patients with metastatic or recurrent esophageal and gastroesophageal (GE) junction cancer.

Secondary objectives:

a) To evaluate the overall response rate (partial response and complete response) of sorafenib.

b) To evaluate the tolerability and adverse event profile of sorafenib in this patient population.

c) To perform an exploratory analysis of differential response between squamous cell carcinoma and adenocarcinoma.

d) To evaluate phosphorylated extracellular signal-regulated kinase (pERK) expression in tumor tissue and correlate with tumor response.

3.0 BACKGROUND AND RATIONALE

3.1 Esophageal cancer

In 2007, there will be an estimated 15,560 new cases of esophageal cancer, with 13,940 estimated deaths.¹ The large majority of esophageal cancers are classified as squamous cell carcinoma (typically arising from the upper/middle thirds of the esophagus) or adenocarcinoma (distal esophagus or gastroesophageal (GE) junction). While squamous cell carcinoma used to be the predominant histological subtype, this is no longer the case in the United States and Western Europe. In the U.S., the incidence of adenocarcinoma of the distal esophagus, GE junction and gastric cardia has increased 4% to 10% per year among U.S. men since 1976 so that it is now the most common histology.^{2,3}

As there is no standard screening procedure for esophageal cancer, 50% of patients present with metastatic disease, where chemotherapy is the mainstay of palliative therapy. Even for patients with localized disease, surgery alone results in 5-year survival of only about 20%, with the remainder of patients developing recurrent disease.⁴ The addition of neoadjuvant chemotherapy or chemoradiotherapy to surgery results in 5-year survival of no more than 25-35%.^{5,6}

For patients with metastatic or recurrent disease, chemotherapy results in responses in 20-40% of patients and median survivals of only 8-10 months.⁷ Prior standard chemotherapy included continuous infusion fluorouracil (5-FU) and cisplatin, the administration of which is cumbersome and requires placement of central intravenous access. Gastrointestinal and other

Amended: 05/12/15

IRB#:09-016A(9)

toxicities are also substantial. Recent investigations have focused on the addition of a third chemotherapy drug (docetaxel) to the standard two-drug regimen, resulting in a modest 0.6 month improvement in overall survival, but at the expense of significant hematologic toxicity (including a 29% rate of febrile neutropenia versus 12% with 5-FU/cisplatin).⁸ Clearly, there is a need for more active and tolerable therapies.

